In none dialysed patients with heart failure, three international controlled trials showed a reduction in cardiovascular morbidity and mortality induced by aldosterone antagonists (spironolactone and eplerenone). Our group participated in the design, conducting and publication of these three studies. The beneficial effects of aldosterone antagonists involve cardiovascular remodelling, including collagen synthesis, as well as effects on endothelial and immune functions. A recent randomised controlled trial conducted in early-stage CKD showed that adding spironolactone to ACE-I or sartans reduces left ventricular mass and arterial stiffness, both of which are independent predictors of cardiovascular events in patients with ESRD. Most clinicians are reluctant to use aldosterone antagonists because of the risk of hyperkalaemia. However, recent studies have demonstrated the safety of spironolactone in anuric ESRD HD patients.

The primary objective is to determine the effects of Spironolactone versus Placebo on a combined endpoint of nonfatal myocardial infarction (MI) and acute coronary syndrome, hospitalization for heart failure, nonfatal stroke, or CV death.

The secondary objective, addressed by the present statistical analysis plan, is to estimate the effect of the treatment group (Spironolactone vs. Placebo) on the Quality of Life (SF-36; KD-QOL and Minnesota) of these patients with the dual pathology: CKD on hemodialysis and established cardiovascular pathology.

Data source(s):

- Data from the ALCHEMIST (Aldosterone antagonist Chronic HEModialysis Interventional Survival Trial) cohort.

2. Analysis objectives

The objective of the analysis is to estimate the effect of treatment group (Spironolactone vs. Placebo) on Quality of Life (QoL) measured by the SF-36 (generic questionnaire), the KD-QOL (kidney failure specific questionnaire) and the Minnesota Heart Failure (heart failure specific questionnaire) at various times during the trial (baseline, 3 months, 1 year, 2 years, 3 years and 4 years).

The analysis will be blinded to the treatment group attributed by randomization.

3. Analysis sample

A total of 750 randomized patients (375 per group) followed for an average of 4 years.

The analysis will be conducted on a intention-to-treat (ITT) and per-protocol (PP) basis, according to the populations defined in the statistical analysis plan of the primary objective (ITT and PP).

4. Study variables

a. Outcome

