- By fitting a linear mixed model, we can also estimate the standard deviation of these coefficients across groups, as well as the standard deviation of individual observations from group means.

Parameter estimates will be reported with their probabilities.

Statistical tests will be two-sided, with $\alpha = 0.05$ as the significance threshold. Each quality-of-life dimension of each questionnaire will be analyzed at this threshold, without correction for multiple testing, in line with standard practice in this field. In fact, the questionnaires are constructed in a paradigm of mutually independent dimensions.

For subjects with QoL data available after an intercurrent event, these events will be treated as time-dependent covariates.

In practice, we will carry out:

On the one hand, for each dimension of quality of life (SF-36, KD-QOL and Minnesota):

- *A model for each quality of life dimension (SF-36, KD-QOL and Minnesota) with a treatment group variable.*
- *A model for each quality of life dimension (SF-36, KD-QOL and Minnesota) with interaction between treatment group and measurement time.*
- *A model for each quality of life dimension (SF-36, KD-QOL and Minnesota) with treatment group variable and confounders.*
- *A model for each quality of life dimension (SF-36, KD-QOL and Minnesota) with treatment group-measurement time interaction and confounding factors.*
- *A model for each quality of life dimension (SF-36, KD-QOL and Minnesota) with treatment group variable, confounders, time-dependent variables and search for treatment group-factor interaction.*
- *A model for each QoL dimension (SF-36, KD-QOL and Minnesota) with treatment group variable, subgroup variables and treatment group-subgroup variable interaction.*

*On the other hand, if a dimension of quality of life (SF-36, KD-QOL and Minnesota) is non-normal, a **transformation by a Log function** will be performed.*

7. Sensitivity analysis

Sensitivity analysis will be performed for each dimension of quality of life, on complete and incomplete data even after imputation rules indicated by the developers of each questionnaire where applicable.

8. Latent Class Trajectory Model : « Group-Based Trajectory Modeling – GBTM »

- Trajectory profile for each dimension of Quality of Life (SF-36, KD-QOL and Minnesota) measured at baseline, 3 months, 1 year, 2 years, 3 years and 4 years.

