Note: all patients with a missing Quality of Life (SF-36, KD-QOL and Minnesota) dimension at all follow-up times will be excluded from the latent class analysis.

a. Identification of Latent Class Trajectories

The various Latent Class Trajectories of each dimension of Quality of Life (SF-36, KD-QOL and Minnesota) are defined using Latent Class Trajectory Models, enabling us to obtain a variable in k trajectories from measured at baseline, 3 months, 1 year, 2 years, 3 years and 4 years.

1. Preliminary description and application conditions

- Measurement time metrics

The time measurement will be indicated transparently and described briefly.

Subjects with complete follow-up will be compared with those with incomplete on relevant characteristics. Significant variables be added as covariates in the Latent Class Trajectory Model.

2. Latent Class Trajectory Model

- These trajectories will be modeled:
 - With SAS, using Proc TRAJ (7), with the following parameters distribution ZIP (Zero Inflated Poisson) for modeling discrete quantitative variables.
- Model comparison and selection of the number of latent classes
 - Using Proc TRAJ in SAS:
 - Best model
Present the evolutionary graph by class of the absolute absolute BIC (Bayesian Information Criterion) values of the Linear, Quadratic and Cubic models.

Note: the best model is the curve model which lies above all the rest.
 - Selecting the number of latent classes
The BIC (Bayesian Information Criterion) is the most suitable selection criterion.
 - The minimum number of patients in each trajectory should be at least 5% of the sample (8).

3. Qualitative characterization and labeling of trajectory classes: description of characteristics at baseline

- Identified trajectories will be described using a graphical representation of the graphical representation of the means (with 95% CI) of the different trajectory classes of the Kellgren stage over time (9) (=> Graph 1, produced using the SAS macro %TRAJPLOTNEW

b. Explanatory factors

✚ **Interest factor**

- ❖ Treatment group (Spironolactone vs Placebo) (blind coded variable) [QL]

✚ **Confounding factors**

- ❖ Age [QT]
- ❖ Sex [QL]
- ❖ Smoking [QL]
- ❖ BMI [QT]
- ❖ Center [QL]
- ❖ Pre-existing CV disease [QL]
- ❖ Pre-existing diabetes at baseline [QL]

c. Factors associated with profiles of each dimension of Quality of Life (SF-36, KD-QOL and Minnesota)

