Bivariate & Multivariate analyses will be used to identify factors associated with profiles of each dimension of Quality of Life (SF-36, KD-QOL and Minnesota).

✚ If K classes =2: binary logistic regressions

✚ If K classes >2: there are several possibilities, depending on the trajectories identified and the objective sought:

- ❖ Several binary logistic regressions with the same reference modality of trajectories
- ❖ Ordinal logistic regression if trajectory classes are ordered
- ❖ Bivariate & Multivariate multinomial logistic regression

The reference modality in these models is defined with the Methodologist and Clinician. If there is no preference, the reference modality will be the one with the largest number of employees.

1. List of variables

- **Variable to be explained:**
 - Profiles of each dimension of Quality of Life (SF-36, KD-QOL and Minnesota)
- **Explanatory factors**
 - **Interest factor**
 - Treatment group (Spironolactone vs Placebo) (blind coded variable) [QL]
 - **Confounding factors**
 - Age [QT]
 - Sex [QL]
 - Smoking [QL]
 - BMI [QT]

- Center [QL]
- Pre-existing CV disease [QL]
- Pre-existing diabetes at baseline [QL]

2. Model used

« Logistic regression model ». Proc logistic from SAS.

- **Bivariate & multivariate model: « Logistic regression model ».**

Application conditions

- Assumption of independence of observations.
- Assumption of logit linearity for quantitative variables.
 - Box-Tidwell test (addition of an interaction term $X \cdot \ln(X)$ in the model): the significance of the interaction indicates a deviation from linearity.
 - Graphical method:
Variable X divided into deciles

Calculation of the proportion $\pi(X)$ of events observed for each decile each decile.

- The graphical representation of $\ln\left(\frac{\pi(X)}{1-\pi(X)}\right)$ as a function of the deciles should have a linear form.

- Model adequacy tests (Pearson or deviance): a significant test may indicate a deviation from linearity.

If the hypothesis is not valid for a quantitative variable X, we can transform it (X^2 , X^3 , \sqrt{X} , $\ln(X)$,...) or discretize it into classes.

- **Model goodness of fit**

- Likelihood ratio test: a significant test indicates that the overall model is more informative than the null model.
- Hosmer-Lemeshow goodness-of-fit test: if the test is significant, the model does not fit the data.

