- The R^2 (Cox-Snell) and pseudo- R^2 (Nagelkerke), which summarize the proportion of variance explained by the model are indicators of model quality. The closer the R^2 is to 1, the better the model.

- ROC curve: the area under the ROC curve is an indicator of model quality. the closer the area under the curve is to 1, the better the model. model.
- Analysis of residuals can, if necessary, reveal outliers. individuals (outliers) that disrupt the construction of the model and model quality.

After the bivariate analysis, we need to select the variables that will enter the multivariate model with $p \leq 0.2$.

Important notes:

- *A model with profiles for each quality of life dimension (SF-36, KD-QOL and Minnesota) with a treatment group variable.*
- *A model with profiles for each quality of life dimension (SF-36, KD-QOL and Minnesota) with interaction between treatment group and measurement time.*
- *A model with profiles for each quality of life dimension (SF-36, KD-QOL and Minnesota) with treatment group variable and confounders.*
- *A model with profiles for each QoL dimension (SF-36, KD-QOL and Minnesota) with treatment group variable, subgroup variables and treatment group-subgroup variable interaction.*

9. Missing data

Imputation does not preserve relationships between variables, and can exert a considerable influence on the distribution of data. For this reason, missing data will not be imputed beyond the rules given by the questionnaire developers.

Statistical analyses will be carried out with **SAS/STAT 9.04.01**. Copyright © 2019 SAS Institute Inc-Cary, NC, USA.

Appendix 1
SF-36

Scoring sheet written by [name]								
Inserm CIC1433 CIC-EC SeleQT								
Description of SF-36 dimensions								
Coding, recoding of items								
Calculation of crude score (CS) taking into account missing data :								
CS = mean of non-missing items*total number of items								
Warning : Crude score can't be calculated if more than 50% of items are missing								
Calculation of normalized score (NS) from 0 to 100 :								
$NS = \{[(CS-C_{BP})/(C_{BM}-C_{BP})]*(N_{BM}-N_{BP})\}+N_{BP}$								
C _{BP} et C _{BM} means respectively HRQoL's worst limit of and HRQoL's best limit of crude score								
N _{BP} et N _{BM} means respectively HRQoL's worst limit of and HRQoL's best limit of normalized score								
NS are normalized such as 0 = worst HRQoL et 100 = best HRQoL								

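### Quality of Life SAP 8.a.1 and 8.c: a variable used to form the trajectory classes may be re-tested against the assigned class, and for such a variable the test is circular

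*SAP*

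**What the plan says.** All references are to the Quality of Life SAP unless stated.

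- **Step 1, section 8.a.1.** "Subjects with complete follow-up will be compared with those with incomplete on relevant characteristics". Then: "Significant variables be added as covariates in the Latent Class Trajectory Model". The characteristics are not named. The text does not say whether a covariate acts on class membership or on the trajectory within a class.
- **Step 2, sections 8.b and 8.c.** "Bivariate & Multivariate analyses will be used to identify factors associated with profiles of each dimension of Quality of Life". The method is logistic regression (binary, ordinal or multinomial) with class as the outcome. The explanatory variables are treatment group and seven confounders: age, sex, smoking, BMI, centre, pre-existing CV disease and diabetes at baseline.
- **Models listed at the end of 8.c.** These include "A model with profiles for each quality of life dimension (SF-36, KD-QOL and Minnesota) with treatment group variable and confounders", and a further model with the subgroup variables of section 5.d. Selection is by the bivariate p-value: "After the bivariate analysis, we need to select the variables that will enter the multivariate model with" p ≤ 0.2.
- **Test level.** Section 6 sets it: "Statistical tests will be two-sided, with $\alpha = 0.05$ as the significance threshold". Section 8 gives no other level for its conclusions.

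No sentence bars a step 1 variable from step 2. None bars treatment from step 1.

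**The concern.** A variable that helps decide which class a patient is put in cannot then be tested against that class as if the class had been observed independently of it.

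The direction of the error depends on a choice the plan leaves open. As a predictor of class membership, the variable's estimated effect, noise included, shifts patients between classes, and the logistic regression finds that shift again. As a covariate of the trajectory, its effect on quality of life is taken out before the classes are formed, so step 2 may miss an effect that is real.

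The purpose of 8.c is to identify factors associated with the profiles. The variables at risk are those linked to incomplete follow-up, and incomplete follow-up will be common: the Context section cites unadjusted mortality of 29% at 2 years and 52% at 5 years, and quality of life is measured up to 4 years. Age, diabetes and CV disease are natural candidates for the screen and are all on the step 2 list.

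**Working it through.** **Inputs from the documents**

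- Level: two-sided 0.05 (section 6).
- Sample size: "A total of 750 randomized patients (375 per group) followed for an average of 4 years" (section 3).
- Times: "measured at baseline, 3 months, 1 year, 2 years, 3 years and 4 years" (section 8), so six.

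The plan states no error rate for the trajectory step. Its only figures to reproduce are the nominal 0.05 and the 750. The 750 agrees with main SAP 1.3.4:

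- Rates −ln(1 − 0.18) = 0.1985 and −ln(1 − 0.126) = 0.1347, so HR = 0.679.
- Events = 4(1.960 + 0.842)² / (ln 0.679)² ≈ 209.
- Mean 2-year event probability = (0.3276 + 0.2361)/2 = 0.282.
- N ≈ 209/0.282 ≈ 741.

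**Why the test is circular**

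With X as a predictor of class membership, the fitted model is Pr(class k | X) ∝ exp(a_k + g_k X), and the patient's data Y have density f_k(Y). The patient goes to the class with the largest Pr(k | X) × f_k(Y). The estimate of g_k is therefore part of the assignment. Regressing assigned class on X recovers that estimate, and the standard error treats class as known. The less Y separates the classes, the more X decides the assignment.

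**Simulation**

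N = 750, up to six visits with drop-out, X unrelated to quality of life, 600 runs per scenario. A Gaussian group-based trajectory model with 2 or 3 classes was fitted, each patient was given the most probable class, and class was regressed on X with a likelihood-ratio test at 0.05. The Monte Carlo standard error is √(0.05 × 0.95/600) = 0.9 points near 5% and √(0.45 × 0.55/600) = 2.0 points near 45%.

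Class separation, intraclass correlation (ICC), drop-out pattern, number of classes, Gaussian outcome and most-probable-class assignment are assumptions. The plan chooses the number of classes by BIC and names a zero-inflated Poisson distribution.

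The table shows the percentage of runs rejecting the null when X is related to drop-out, so that it passes the screen.

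| Scenario | Entropy | X left out | X predicts class | X at trajectory level | X tested inside class model |
|---|---|---|---|---|---|
| 2 classes, 3 SD apart | 0.97 | 4.3 | 4.5 | 3.8 | 4.3 |
| 2 classes, 2 SD | 0.87 | 4.5 | 7.7 | 3.8 | 5.0 |
| 3 classes, 2 SD | 0.89 | 5.2 | 10.2 | 4.5 | 4.3 |
| 2 classes, 1.5 SD | 0.73 | 4.7 | 12.0 | 4.3 | 4.7 |
| 3 classes, 1.5 SD | 0.77 | 5.2 | 18.7 | 3.5 | 5.0 |
| 2 classes, 1 SD | 0.48 | 3.7 | 25.8 | 1.3 | 5.8 |
| 3 classes, 1 SD | 0.56 | 6.0 | 46.7 | 0.7 | 6.0 |
| No true classes, 2 fitted, ICC 0.7 | 0.76 | 6.2 | 12.3 | 19.2 | 6.3 |
| No true classes, 3 fitted, ICC 0.3 | 0.56 | 7.2 | 44.3 | 6.0 | 5.7 |
| 2 classes that part only late | 0.35 | 23.5 | 74.2 | 20.8 | 3.8 |

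Over all scenarios run:

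- X left out: 3.7 to 7.2%, except 23.5% in the last row.
- X at trajectory level: 0.2 to 20.8%.
- X tested inside the class model: 3.8 to 6.8%.
- A randomised treatment indicator not entered in the class model: 2.8 to 6.3%.

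**Loss of a real effect**

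A separate run used 700 patients and a true 5-point effect, the difference section 5.c calls clinically significant. With the variable entered at trajectory level, the step 2 odds ratio fell from 1.35 to 0.99 and power from 51% to 5%. This rests on 150 runs, so the 51% has a standard error of √(0.51 × 0.49/150) = 4 points.

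**The case against.** Four points can fairly be made for the plan.

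1. **Overlap is not stated.** Section 8.a.1 speaks only of relevant characteristics and does not link them to the 8.b list. This stands: overlap is an inference, though a likely one, since step 2 with its subgroup variables covers most baseline factors the plan names.
2. **No error rate follows from the text.** The plan gives neither class separation nor covariate role, and with very well separated classes there is no inflation (4.5%). This stands. A reader might infer one inflated error rate for this plan, but the documents do not support one.
3. **The consequence is limited.** The treatment effect on quality of life is estimated by the linear mixed model that section 6 calls the principal analysis, which this rule does not touch. Main SAP 1.2 lists quality of life under Part 2, whose objectives are for hypothesis generation. This stands and limits the weight of the point.
4. **Covariates related to drop-out have a reason to be in the model.** Leaving them out is not a sure cure: 23.5% in the late-parting scenario. This stands too, and it shapes the fix. It does not rescue the second test, which was at 74.2% in that same scenario.

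None of this removes the fault. An analyst following 8.a.1 and 8.c as written may test a variable against a class that the variable helped to define.

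**Conclusion.** The point holds for variables that are both screened into the class-forming model and tested in 8.c. For these the logistic p-value is not valid. Under the simulation assumptions, type I error runs from about 5% with very well separated classes to over 40% with poorly separated ones if the variable predicts class membership. The late-parting scenario was more extreme still. At trajectory level, rejection was about 0 to 20%, often below nominal, and a real effect can vanish. As the plan does not fix the role, even the direction of the error is open.

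A reader might infer that the plan's test of spironolactone on the trajectories is invalid. The documents do not support that. Treatment is listed as the factor of interest, apart from the confounders, and nothing says it will be screened. When it stayed out of the class model its test kept close to 5%. It would be affected only if follow-up completeness differed significantly by arm and treatment was then entered.

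The fault should be corrected, but it is confined to a secondary, hypothesis-generating step.

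**What to change.** In 8.a.1, replace the sentence on adding significant variables with wording to this effect:

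> Treatment group will not enter the model that forms the trajectory classes. For any other covariate kept in that model, its role (predictor of class membership or covariate of the trajectory) will be stated. Its effect will be tested and reported from that model, and it will not be re-tested by logistic regression on assigned class.

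Add the matching exclusion to 8.c. Naming the characteristics to be compared would make the rule complete.

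The cost is SAP wording, slightly more modelling work, and a results table in which those covariates come from a different model than the rest.

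An alternative is to describe completers and non-completers, keep every covariate out of the class model, and adjust in 8.c. It is simpler, but it does not guarantee the 5% level when a variable drives drop-out and the classes separate late.

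### The p ≤ 0.2 entry rule for the adjusted QoL trajectory models exempts neither treatment nor centre, and conflicts with the adjusted models listed directly below it

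*SAP*

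**What the plan says.** Section 8 of the QoL SAP groups patients into trajectory classes for each QoL dimension. Section 8.c then uses logistic regression to find the factors associated with class membership.

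- **Candidate variables (8.c.1).** One list of explanatory factors holds treatment group, under its own label as the factor of interest, and seven confounders: age, sex, smoking, BMI, centre, pre-existing CV disease and diabetes.
- **Entry rule (8.c.2).** "After the bivariate analysis, we need to select the variables that will enter the multivariate model", the criterion being p ≤ 0.2. No variable is exempted.
- **Models to be fitted (*Important notes*, 8.c.2).** Directly after the rule, the list includes a model with treatment alone and then "A model with profiles for each quality of life dimension (SF-36, KD-QOL and Minnesota) with treatment group variable and confounders". Neither depends on a p-value.
- **Centre (section 4).** Unless otherwise indicated, the treatment effect is adjusted for centre, which is also to be grouped as in the principal analysis. Section 1.3.3 of the main SAP confirms that randomisation was stratified by centre.
- **Principal QoL analysis (section 6).** A linear mixed model is fitted for each dimension, with treatment alone and with treatment plus confounders. No p ≤ 0.2 screen is stated there.

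**The concern.** The entry rule and the notes cannot both be followed when treatment or a listed confounder has a bivariate p above 0.2. The notes ask for an adjusted treatment model in every dimension; the rule, taken at its word, removes the variable. Two programmers working from this section could produce different adjusted results from the same data.

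Two things are at stake. If treatment itself is screened, the randomised factor can disappear from its own adjusted model, and where it stays it has been selected on its own p-value. If only the confounders are screened, the stratification factor can be lost and the adjustment set is chosen from the outcome data, separately for each score. Bivariate screening is a poor way to choose covariates in a randomised comparison, since what is adjusted for should not depend on the outcome data.

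**Working it through.** The SAP gives no error rate or power for this analysis, so there is no figure of its own to reproduce. The check sizes each reading of the rule.

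**Inputs**
- Scores, counted from section 4 of the QoL SAP: 10 (SF-36) + 3 (KD-QOL) + 4 (Minnesota) = 17.
- Screening threshold, 8.c.2: p ≤ 0.2. Taken as two-sided, this means |z| ≥ 1.2816.
- Significance level, section 6: two-sided 0.05, with no multiplicity correction.
- Assumption: the adjusted test statistic for treatment is close to the bivariate one, which is reasonable for a randomised factor.

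**Reading A: treatment is screened as well, no true effect**
- Kept: 0.20 of dimensions, so 0.20 × 17 = 3.4 expected. Dropped: 0.80 × 17 = 13.6.
- The screen is two-sided, so half of those kept (0.10 × 17 = 1.7) point towards harm.
- P(p < 0.05 given kept) = 0.05 / 0.20 = 25%.
- Unconditionally, 0.20 × 0.25 = 5% per dimension, or 0.05 × 17 = 0.85 expected, the same as without a screen. The rule does not create more false positives; it leaves out the null adjusted results that would put them in context.

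**Reading A, with a true effect.** Take z ~ N(θ, 1), kept if |z| ≥ 1.2816 (2,000,000 draws per value):

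| θ | kept | mean z when kept | ratio to θ |
|---|---|---|---|
| 1.0 | 40% | 1.885 | 1.88 |
| 1.5 | 59% | 2.147 | 1.43 |
| 2.0 | 76% | 2.401 | 1.20 |
| 2.8 | 94% | 2.934 | 1.05 |

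A modest effect would therefore be dropped in 60% (θ = 1.0) to 24% (θ = 2.0) of dimensions, and overstated about 1.9- to 1.2-fold where kept.

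**Reading B: only the confounders are screened.** Treatment stays in all 17 adjusted models and none of the figures above arises. Two faults remain:
- Centre is one of the seven screened variables. Where it is unrelated to the profiles it fails the screen with probability 0.80, although section 4 makes adjustment for it the default.
- Each of the 17 scores gets its own data-chosen subset of seven covariates, out of 2^7 = 128 possible subsets. The phrase about confounders in the notes then has no fixed meaning.

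**After the fix.** Treatment is estimated in 17 of 17 adjusted models, each at a nominal 5%, with no selection on its own p-value.

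**The case against.** The strongest reply is that treatment was never meant to be screened. It has its own label, apart from the confounders, and the notes plan both an unadjusted and an adjusted treatment model for each dimension without condition. One could even read the section as describing two exercises: a screened search for associated factors and, separately, the fixed treatment models in the notes.

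Much of this stands. A reader might infer that the adjusted drug effect will be reported only where it looks promising. The documents do not support that: the SAP nowhere says that treatment is screened, the notes point the other way, and a two-sided screen passes apparent harm as readily as benefit. Nor would null dimensions be hidden altogether, because the unadjusted trajectory model and the principal mixed model cover every dimension.

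What does not stand is the idea that the text settles the matter. The rule applies to the variables without exception and comes immediately before the notes, with nothing to say which governs. The proviso in section 4 does not rescue it either, since 8.c.2 never says that it overrides adjustment for centre.

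Two further arguments are fair. A fixed covariate list would not make odds ratios fully comparable across scores, because the number of classes and the reference class also depend on the data. And the rule in 8.a.1, "Significant variables be added as covariates in the Latent Class Trajectory Model", follows a comparison of subjects with complete and incomplete follow-up. It addresses missingness and is not a screen on the treatment effect, so it does not support this point.

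**Conclusion.** The entry rule in 8.c.2 is unreconciled with the notes below it and with the default adjustment for centre, and it should be replaced. The 80%, 25% and 1.9-fold figures hold only if treatment itself is screened and its adjusted and bivariate statistics nearly agree; they are not a forecast of what the analysts will do. On the milder reading, the harm is possible loss of the stratification factor and data-driven adjustment that differs between the 17 scores.

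The scope is limited to the adjusted models of a supporting QoL trajectory analysis. The trial's primary endpoint, the principal QoL mixed model and the unadjusted trajectory models are not affected. The correction is worth making because it is cheap and removes an avoidable ambiguity from a plan whose stated aim is to estimate the treatment effect on QoL.

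**What to change.** In section 8.c.2, delete the p ≤ 0.2 selection. State instead that treatment group and centre (grouped as in the principal analysis) are kept in every adjusted trajectory model, and that one set of baseline covariates, named in advance from those already listed, is used for all 17 scores. In the notes, say that the confounders are this set.

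The edit is a few sentences. It leaves some weak covariates in the models. The more serious cost is stability: a class may hold as little as 5% of the sample, which is 0.05 × 750 = 37.5, or about 38 patients at the planned size if all are analysed. All seven confounders may be too many for a multinomial model with such a class. The fixed list may therefore need to be short, but it should be chosen before the data are seen and not by p-value.

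### QoL SAP section 8.c asks for a treatment-by-time interaction in a logistic model of trajectory class, but each patient has one class for all times, so the term has no meaning

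*SAP*

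**What the plan says.** Section 8.a of the QoL SAP derives the trajectory classes for each QoL dimension, "enabling us to obtain a variable in k trajectories from measured at baseline, 3 months, 1 year, 2 years, 3 years and 4 years". The result is one class per patient and dimension, and it summarises the whole series of scores.

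Section 8.c makes that class the dependent variable. The model type depends on the number of classes: "If K classes =2: binary logistic regressions", and several binary, ordinal or multinomial models when there are more than two. The procedure is "Proc logistic from SAS", and the first application condition is "Assumption of independence of observations". The explanatory factors in sections 8.b and 8.c.1 are treatment group and baseline confounders. Measurement time is not among them, and no clustering term, GEE or random effect is named.

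The Important notes that close section 8.c.2 then list four models. One is "A model with profiles for each quality of life dimension (SF-36, KD-QOL and Minnesota) with interaction between treatment group and measurement time". The other three are class on treatment, class on treatment plus confounders, and class on treatment by subgroup.

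Section 6.A.2 has a similar treatment-by-time line for the linear mixed models, with and without confounders. There the outcome is a score measured at each visit.

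**The concern.** An interaction with measurement time needs an outcome that can differ between times. Trajectory class cannot, because it is fixed once for the whole follow-up. The line therefore conflicts with the outcome, the variable list and the independence condition of its own section.

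A programmer who has to deliver it must either depart from the SAP or build a file with each patient's class repeated on every visit row. The second course gives an interaction test that says nothing about the drug, and treatment tests that count the same patient several times. The line applies to 17 scores (10 SF-36, 3 KD-QOL, 4 Minnesota), and section 6.A.2 applies no multiplicity correction across QoL dimensions.

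**Working it through.** **Inputs from the documents.** Six measurement times: 0, 0.25, 1, 2, 3 and 4 years (QoL SAP sections 2 and 8). 750 patients, 375 per arm (section 3). Two-sided 0.05 (section 6.A.2). **Assumptions, not in the documents:** two classes; 30% of patients in the class of interest in both arms under no effect; 30% against 20% under an effect; the drop-out patterns in step 5.

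**1. Nominal level.** With one row per patient, class on treatment, 2,000 simulated trials under no effect rejected in 5.0%, equal to the stated 0.05.

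**2. Interaction, one row per patient.** There is no time variable in the file, so the term cannot be formed.

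**3. Interaction, rows stacked, complete visits.** The class-by-arm table is the same at every visit, so the log odds ratio is the same too. With 30% against 20% it is ln[(0.2/0.8)/(0.3/0.7)] = ln(0.583) = -0.539 at each of the six times, and every difference between times is 0. In simulation the largest interaction coefficient was about 2e-14 in size, both under no effect (2,000 runs) and under 30% against 20% (300 runs). The interaction was rejected in 0% of runs.

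**4. Treatment test, rows stacked, complete visits.** With m identical rows treated as independent, the standard error of a main-effect or visit-averaged test shrinks by sqrt(m), so its type I error is 2 × P(Z > 1.96/sqrt(m)):

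| Rows m | 1 | 2 | 3 | 4 | 5 | 6 |
|---|---|---|---|---|---|---|
| Type I error | 5.0% | 16.6% | 25.8% | 32.7% | 38.1% | 42.4% |

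Simulation with six rows gave 41.8%. The treatment coefficient inside the interaction model depends on how time is coded:
- Reference coding: it uses only the rows of the reference visit, one per patient. Simulated 5.0%.
- Linear time: it is the effect at time 0. The mean time is 10.25/6 = 1.708 and the sum of squares about it is 30.0625 - 6 × 1.708² = 12.55. The naive variance is 1/6 + 1.708²/12.55 = 0.399 of the correct one, so the error is 2 × P(Z > 1.96 × sqrt(0.399)) = 2 × P(Z > 1.238) = 21.6%. Simulated 21.2%.

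**5. Rows stacked, missing visits.** Let r(a,c) be the share of arm a, class c, that still has a row at time t. The log odds ratio at t is the true one plus ln{[r(1,1)/r(1,0)]/[r(0,1)/r(0,0)]}. Any interaction is that second term, which concerns retention only.
- Drop-out unrelated to class or arm (15% per visit from the third visit): interaction rejected in 0.0% (categorical time) and 0.5% (linear); averaged treatment test rejected in 38.9% under no effect.
- Drop-out by class only (30% against 10%): interaction rejected in 0.1% and 3.9% under no effect, and in 0.3% and 3.7% with 30% against 20%; averaged treatment test rejected in 36.1% under no effect.
- Drop-out by class and arm together (15% on treatment and 35% on control in the class of interest, 10% elsewhere): the retention term is ln(0.85/0.65) = 0.268 at the third visit and 4 × 0.268 = 1.07 at the sixth. The interaction was rejected in 93.6% (categorical) and 100% (linear) of 500 runs, with no treatment effect on class.

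**The case against.** The strongest reply is that the plan nowhere says visits will be stacked. Section 8.c lists no time variable and requires independent observations, so a statistician who follows it has one record per patient and simply cannot fit this line. That stands. The defect is a line that cannot be executed, and a reader who inferred that the plan carries a 42% type I error would go beyond the documents. The 42% also needs six complete visits for every patient and a main-effect or visit-averaged test. Six complete visits are doubtful: the main SAP (section 1.3.1) gives 2 years of average follow-up against 4 in the QoL SAP (section 3), background mortality is cited as 29% at 2 years, and missing questionnaires are not imputed. At 2 years a patient has four of the six times, which gives about 33%.

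A reader might also infer that the interaction would always be reported as absent. Step 5 shows otherwise: if drop-out depends on class and arm together, the error would be a false interaction.

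Finally, the inference is covered elsewhere. The same list already holds the three valid class models, and section 6.A.2 holds the treatment-by-time mixed models. That also stands. It limits the harm and makes deletion free, but it does not make the line fittable.

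**Conclusion.** The point holds as a minor one. The interaction is undefined with one record per patient. On stacked rows it is zero with complete visits and otherwise reflects retention, so under no data layout does it estimate a change of drug effect over time. This follows from the definition of the class and needs no assumption about prevalence or effect size.

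The error rates are conditional on a naive stacked analysis, which the plan does not prescribe. For a main-effect or visit-averaged treatment test they run up to about 42% with six complete visits and about 33% with four. For the treatment coefficient of the interaction model they are about 21% with linear time and 5% with reference coding. The rejection rates under drop-out rest on the assumed patterns and show direction rather than a forecast.

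Quality of life is secondary objective (i) in section 1.2 of the main SAP, under objectives meant for hypothesis generation. Section 8 follows the QoL principal analysis. No primary, hierarchical or safety conclusion is touched. The likeness to the mixed-model line in section 6.A.2 suggests a carry-over, but the document does not say so.

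**What to change.** Delete the treatment-by-measurement-time line from the Important notes in section 8.c.2. Add one sentence stating that all trajectory-class models use one record per patient and dimension. Add a cross-reference saying that change of treatment effect over time is assessed in the section 6.A.2 linear mixed models with treatment-by-time interaction. The other three class models stay as listed.

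The cost is one deleted line and two added sentences. No data, analysis or information is lost.
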